9.3.1.1. Thrombosis Risk Factors

To assess risk factors for MACE and to allow for the estimation of the proportion of patients with approved indications (i.e. RA, PsA, UC, pcJIA) who have with ≥1 thrombosis risk factors and are prescribed tofacitinib, the following thrombosis risk factors will be evaluated at baseline and/or, for some risk factors, within specific time periods prior to index date as specified below:

- o Age
- Smoking status
- Use of combined hormonal contraceptives or hormone replacement therapy within 3 months of index date
- o Previous VTE
- o History of MI within previous 3 months prior to index date

- o History of heart failure
- History of hypertension
- o History of malignancy (using all available data)
- Diabetes
- Inherited coagulation disorders

9.3.2. Definition of On-Label and Off-Label Use for Assessing Utilization Patterns

The following table summarizes the date tofacitinib was approved in the US and the approved dose for each of the three approved indications.

Table 2. Summary of approved indications and dosages for tofacitinib in the US

Indication	Date approved in the US	Approved dose	Limitations for use	
RA	06 Nov 2012	5 mg immediate-release tablets twice daily	Not recommended for use in combination with biologic	
	24 Feb 2016	11 mg prolonged release tablets once daily	DMARDs or potent immunosuppressants such as azathioprine and cyclosporine	
PsA	14 Dec 2017	5 mg immediate-release tablets twice daily	Not recommended for use in combination with biologic DMARDs or potent immunosuppressants such as azathioprine and cyclosporine	
	14 Dec 2017	11 mg prolonged release tablets once daily		
UC	30 May 2018	5 mg or 10 mg immediate- release tablets twice daily	Not recommended for use in combination with biological	
	12 December 2019	11 mg or 22 mg prolonged release tablets once daily	therapies for UC or potent immunosuppressants such as azathioprine and cyclosporine	
рсЛА	25 September 2020	5 mg immediate-release tablets twice daily or weight-based equivalent twice daily (tablet or oral solution)	Not recommended for use in combination with biologic DMARDs or potent immunosuppressants such as azathioprine and cyclosporine	

pcJIA = polyarticular course juvenile idiopathic arthritis; PsA = psoriatic arthritis; RA = rheumatoid arthritis; UC = ulcerative colitis; US = United States

To evaluate indication for use, all patients' to facitinib use will be classified as onlabel indication, off-label indication or unknown indication associated with the first to facitinib prescription during the observation period. Thus, for the purpose of this analysis, on-label indication for use of tofacitinib will be defined, based on the date of the first prescription, as a prescription of the drug to:

- 1. An adult (patients aged ≥18 years), AND
- 2. After November 2012, a patient whose first tofacitinib prescription occurred after a diagnosis of RA (defined as either as having ≥ 1 inpatient or ≥ 2 outpatient RA diagnosis codes on two unique calendar days, with at least one from a rheumatologist), OR
- 3. After December 2017, a patient whose first tofacitinib prescription occurred after a diagnosis of PsA (defined as either as having ≥ 1 inpatient or ≥ 2 outpatient PsA diagnosis codes on two unique calendar days, with at least one from a rheumatologist), OR
- 4. Between May 2018 and July 2019, a patient whose first tofacitinib prescription occurred after a diagnosis of UC (defined as the first UC diagnosis code from an inpatient visit or after the second UC diagnosis code from an outpatient visit), OR
- 5. After July 2019, a patient whose first tofacitinib prescription occurred after a diagnosis of UC (as defined above) AND after evidence of prior TNFi use (i.e. using all available data, a prescription for ≥1 TNFi agent prior to first tofacitinib prescription), OR
- 6. After September 2020, a patient aged ≥2 years whose first tofacitinib prescription occurred after a diagnosis of pcJIA (defined as either as having ≥ 1 inpatient or ≥ 2 outpatient pcJIA diagnosis codes on two unique calendar days, with at least one from a rheumatologist)

In contrast, off-label indications will be defined as use of tofacitinib among patients with other diagnoses (i.e. lack of diagnosis codes for RA, PsA, UC or JIA) not fulfilling any of the conditions outlined above. If off-label use among non-approved indications occurs, it is expected that tofacitinib will be more likely used among patients with other non-approved rheumatic conditions (e.g. psoriasis, ankylosing spondylitis) or other non-approved IBD conditions (e.g. Crohn's disease). Thus off-label indications will be identified by broadly targeting diagnosis codes for other non-approved rheumatic and IBD conditions. Additionally, if the indications for which tofacitinib is prescribed cannot be determined from the available data, these will be classified as unknown indications and will evaluated separately as described in Section 9.7.1.

Among patients with on-label indications, to facitinib dose will be assessed. For each of these patients, every to facitinib prescription will be classified as on-label or off-label based on the labeled dose for the patient's indication at the time of prescription. Thus, for the

purposes of this analysis, on-label dose of tofacitinib will be defined, based on each tofacitinib prescription, using the following criteria:

- 1. Between November 2012 and November 2017, a prescription of tofacitinib 5 mg twice daily occurring only after a diagnosis of RA (as defined above)
- 2. Between February 2016 and November 2017, a prescription of tofacitinib 11 mg once daily occurring only after a diagnosis of RA (as defined above)
- 3. After December 2017, a prescription of tofacitinib 5 mg twice daily or 11 mg once daily occurring only after a diagnosis of either RA or PsA (as defined above)
- 4. After May 2018, a prescription of tofacitinib 5 mg twice daily occurring only after a diagnosis of either RA, PsA or UC (as defined above)
- 5. After May 2018, a prescription of tofacitinib 10 mg twice daily occurring only after a diagnosis of UC (as defined above)
- 6. After December 2019, a prescription of tofacitinib 11 mg once daily or 22 mg once daily occurring only after a diagnosis of UC (as defined above)
- 7. After September 2020, a prescription of tofacitinib 5 mg twice daily occurring only after a diagnosis of RA, PsA, UC or pcJIA.

For each approved indication of tofacitinib (i.e. RA, PsA, UC, pcJIA), the proportion of tofacitinib prescriptions with off-label dosing will be estimated as described in Section 9.7.1.

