9.3.6. Endpoints of Interest

To assess tofacitinib utilization patterns, the main endpoint of interest to be captured in the interim and final study reports will be the indication for tofacitinib use, classified as on-label, off-label, or unknown, based on medical events (diagnoses and/or medication use) identifiable around the time of the first ever tofacitinib prescription. The date of first prescription of tofacitinib during the study period is the index date as described in Section 9.3.4.1. All patients' tofacitinib use will be classified as on-label indication, off-label indication or unknown indication according to the first prescription of tofacitinib received, regardless of later prescriptions. The on-label, off-label and unknown indication classifications will be made based on the authorized indication(s) as of the index date.

For the active surveillance portion of the study, the safety events of interest (to be defined via ICD-code based algorithms in the SAP) which will also be captured in the interim and final study reports include the following:

- Malignancy, excluding NMSC
- Lung cancer
- Lymphoma
- NMSC
 - Serious infections
 - Opportunistic infections (e.g. tuberculosis)
 - HZ reactivation

- MACE
- VTE (DVT and PE)
- Myocardial Infarction (MI)
- Hepatic events
- PML (PML)
- GI perforations
- ILD
- Fractures
- Surgery for UC (e.g. colectomies, partial colectomies, and proctocolectomies; full list of procedures to be detailed in SAP)
- Death

Of note, due to limitations related to the Marketscan database, only in-hospital deaths can be captured (outcome will be defined via an algorithm currently under development, details of which will be outlined in the SAP). Deaths occurring in other environments such as home, non-hospital institutions, etc., cannot be captured.

The above list of safety endpoints may be extended with additional sub-diagnoses or new health-related outcomes as agreed to by study researchers and Sponsor before the interim reports and final study report. These decisions will be made prior to initiation of analyses and documented in the SAP kept on file by the Sponsor.

In addition, the final study report will include the number of tofacitinib-exposed pregnancies.

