9.7.1. Assessment of tofacitinib utilization patterns

Categorical variables will be summarized using frequencies and proportions; continuous variables will summarized using means with standard deviations and/or medians with interquartile ranges, as appropriate. Age will be reported as a continuous variable and in clinically relevant categories, to identify off-label pediatric use (e.g. use in patients younger than 18 years prior to September 2020 and who do not have a pcJIA diagnosis) and use among elderly patients (i.e. 65 years or older).

The proportions of patients with an on-label, off-label, or unknown tofacitinib indication will be estimated with corresponding 95% confidence intervals (CIs). Patients who are prescribed tofacitinib for on-label, off-label and unknown indications will be described in terms of demographics (age, sex), comorbidities, prior and current medications (in terms of comedications not recommended for use while on tofacitinib i.e. biologic DMARDs, biologic therapies for UC or potent immunosuppressants such as azathioprine and cyclosporine as described in Table 2), as well as prescribed DD and duration of tofacitinib therapy. As it is expected that tofacitinib is more likely to be used off-label in non-approved rheumatic (e.g. psoriasis, ankylosing spondylitis) and IBD conditions (e.g. Crohn's disease), to identify off-label indications, diagnosis codes for other non-approved rheumatic and IBD conditions will be targeted. Among patients with on-label (approved) indications (i.e. RA, PsA, UC, pcJIA), tofacitinib dose will be assessed (as described in Section 9.3.2) and classified as on-label dose or off-label dose according to each prescription of tofacitinib. The proportion of tofacitinib prescriptions with off-label dosing, stratified by approved indication, will be estimated.

To further assess on-label/off-label use of tofacitinib, the proportion of TNFi-naïve UC patients prescribed tofacitinib prior to 01 July 2019 (on-label) and post 01 July 2019 (off-label) will also be estimated and described. Additionally, to further understand off-label dosing among patients with non-UC approved indications such as RA, PsA and pcJIA, the proportions of non-UC patients on 10 mg twice daily/22 mg once daily therapy will also be estimated and reported.

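### Section 9.3.2: the adult condition in on-label rule 1 cancels the pcJIA rule from age 2, and dose rule 7 omits the weight-based pcJIA dose that Table 2 lists as approved

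*Protocol*

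**What the plan says.** **Indication.** Protocol Section 9.3.2 defines on-label indication by a numbered list. Rule 1 reads "An adult (patients aged ≥18 years), AND". Rules 2 to 6 follow, joined by OR, for RA, PsA, UC (two periods) and pcJIA. Rule 6 reads "After September 2020, a patient aged ≥2 years whose first tofacitinib prescription occurred after a diagnosis of pcJIA". Off-label indication is described as "use of tofacitinib among patients with other diagnoses (i.e. lack of diagnosis codes for RA, PsA, UC or JIA", with the added words that none of the on-label conditions is fulfilled. A third class, unknown, is kept for indications that cannot be determined from the data.

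**Intent elsewhere.** Section 9.3.6 states: "The on-label, off-label and unknown indication classifications will be made based on the authorized indication(s) as of the index date". Section 9.7.1 gives as its example of off-label pediatric use "use in patients younger than 18 years prior to September 2020 and who do not have a pcJIA diagnosis".

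**Dose.** Dose is assessed only in patients with an on-label indication, and each of their prescriptions is "classified as on-label or off-label based on the labeled dose" for the indication at that time. Dose rule 7 reads "After September 2020, a prescription of tofacitinib 5 mg twice daily occurring only after a diagnosis of RA, PsA, UC or pcJIA". Section 7 and the abstract likewise give 5 mg twice daily as the pcJIA dose, and Section 7 calls it the only approved regimen. Table 2, in the same Section 9.3.2, lists for pcJIA either 5 mg tablets twice daily or a weight-based equivalent twice daily, as tablet or oral solution.

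**The concern.** Indication class is the main utilization endpoint (Section 9.3.6), and Section 9.3.2 promises an off-label dosing proportion for each approved indication, with pcJIA named. A programmer who codes the list as laid out would exclude every child with pcJIA from the on-label class, although pcJIA is the one indication the protocol describes as approved for children. Those children would then have no dose result. A programmer who repairs rule 1 but codes rule 7 as written would admit the children and then count an approved weight-based dose as off-label.

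These are contradictions between statements the protocol makes. They are not details left to the analysis plan.

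**Working it through.** No sample size or error rate is involved. The check is a truth table of the indication rules, followed by a comparison of the dose texts.

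**1. Benchmark.** Section 7 describes the RA, PsA and UC approvals as for adults and the pcJIA approval as from age 2. After all approvals, the on-label result should therefore be (adult AND (RA or PsA or UC)) OR pcJIA. Prior TNFi use is assumed for UC, as rule 5 requires after July 2019.

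**2. Truth table**, first prescription after 25 September 2020, child taken as age 10 and adult as age 30:

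| Patient | Benchmark | Rule 1 governs rules 2–6 (as laid out) | Rule 1 governs rule 2 only | Rule 1 governs rules 2–5 |
|---|---|---|---|---|
| Adult, any of the 4 diagnoses | on | on | on | on |
| Child, RA | not | not | not | not |
| Child, PsA | not | not | **on** | not |
| Child, UC | not | not | **on** | not |
| Child, pcJIA | on | **not** | on | on |
| Wrong cells of 8 | – | 1 | 2 | 0 |

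The eight cells are 2 ages × 4 diagnoses. Under the layout as written, the age limit in rule 6 has no effect. Only (age ≥18 AND any of rules 2–5) OR rule 6 reproduces the benchmark.

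**3. Where the child with pcJIA goes instead.** The unknown class does not fit, because the indication is coded. The off-label sentence has two parts: no code for RA, PsA, UC or JIA, and none of the conditions fulfilled. The child meets the second part and fails the first. If the bracket about codes is binding, the child is unclassified; if it is only descriptive, the child is off-label. Either result is wrong for approved use.

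**4. Is the bracket binding?** Section 9.7.1 calls TNFi-naïve UC patients prescribed tofacitinib after 01 July 2019 off-label, and those patients carry UC codes. So the protocol does not itself treat the bracket as a hard condition. Left in place, the bracket would still be a problem after rule 1 is repaired. Children with RA, PsA or UC, and TNFi-naïve adults with UC after July 2019, are not on-label but have a listed code, so a strict coder would leave them unclassified too.

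**5. Dose texts side by side for pcJIA:**

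| Place | 5 mg twice daily | Weight-based equivalent, tablet or oral solution |
|---|---|---|
| Table 2 | approved | approved |
| Dose rule 7 | on-label | not admitted |
| Dose rules 1–6 | do not mention pcJIA | do not mention pcJIA |
| Section 7, abstract | approved | not mentioned; Section 7 says only 5 mg twice daily |

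A pcJIA fill at another weight-based dose fails all seven dose rules although Table 2 lists it as approved.

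**6. How the two faults interact.** Because dose is assessed only in patients with an on-label indication, children with pcJIA never reach rule 7 under the layout as written. For them, the rule 7 fault takes effect once rule 1 is repaired, so both need correcting together.

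**7. Exposure to the fault.** The affected calendar period runs from 25 September 2020 to 30 June 2025, which is 1,740 days counted inclusively, or about 57 months. This is calendar time, not patients or fills.

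**The case against.** **The intent is plain.** Rule 6 carries its own age limit, which would be pointless under rule 1. Section 9.3.6 ties classification to the authorized indication, and Section 9.7.1 sets pcJIA apart when it describes pediatric off-label use. All of this stands, and it is why the point is minor. It does not remove the point: Section 9.3.2 is the operative definition, and its stated logic gives a different class. That section also still introduces Table 2 as covering three approved indications when the table lists four, which suggests that pcJIA was not carried through consistently.

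**The lead-in to the dose rules already sets the labeled dose as the standard.** It does, and Table 2 states that dose. But the criteria that follow are given as the definition for this analysis and leave the weight-based dose out, and Section 7 supports the omission.

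**The analysis plan can settle it.** Section 9.3 leaves detailed definitions such as codes to that plan. Here the protocol has already fixed the rule, and Section 9.7 says that major modifications of endpoint definitions would be reflected in a protocol amendment.

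**Stronger readings that the document does not support.**
- A reader might infer that a child with pcJIA necessarily falls into no class. That needs the code bracket to be binding, and Section 9.7.1 shows that it is not applied that way to UC.
- A reader might infer that children with PsA or UC become on-label. That needs AND to bind rule 2 alone, a strained reading that no text supports, since Section 7 limits both approvals to adults.
- A reader might infer a material distortion of the overall on-label proportion. Nothing in the protocol allows that to be shown.

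**Conclusion.** The point holds in two parts. As laid out, rule 1 cancels the age limit in rule 6. A child with pcJIA treated after 25 September 2020 is then off-label or unclassified, depending on how the off-label bracket is read, and gets no dose result. Separately, rule 7, Section 7 and the abstract contradict Table 2 on the approved pcJIA dose.

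The effect is confined to pcJIA users after September 2020 in the drug utilization component. The one tofacitinib count given, 11,857 patients from 2016 to 2018, predates the pcJIA approval and is not split by indication, so the effect on the proportions cannot be sized. The active surveillance cohorts are limited to adults with UC, so the malignancy objective and the other incidence rates are untouched. Severity is minor. The conclusion assumes that the rules are coded as the list is laid out and that Table 2 is the correct statement of the approved dose.

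**What to change.** - **On-label indication:** define it as (age ≥18 AND any of rules 2–5) OR rule 6.
- **Off-label indication:** define it as a determinable indication that does not meet the on-label rule, and drop the condition on absence of RA, PsA, UC or JIA codes. Children with RA, PsA or UC, and TNFi-naïve UC patients after July 2019, are then off-label, consistent with Section 9.7.1. Unknown stays for indications that cannot be determined.
- **Dose rule 7:** for pcJIA, add the weight-based equivalent twice daily (tablet or oral solution) in Table 2's terms. Do not accept any lower dose as on-label, because Table 2 does not say that.
- **Section 7 and abstract:** align the pcJIA dose with Table 2.
- **Section 9.9:** add one line that the weight-based dose may not be verifiable if body weight is unavailable in the claims data. Section 9.4.1 does not describe body weight among the data held.

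The cost is a text edit, with no new data. The remaining weakness is that, without body weight, an incorrect weight-based dose could pass as on-label, which is why the limitation should be stated.

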9.2.1.2. Active surveillance study

The active surveillance population to be used for the estimation of the incidence rates of the safety events of interest will be a subset of the population described above, and will include all adult UC patients aged ≥18 years who are enrolled in the Marketscan database from the time of approval of tofacitinib for UC in the US (May 2018) through to the end of data collection (June 2025) for the study. UC patients will be identified via ICD-10 codes listed in Table 1. Using all available data, UC patients must have at least one UC diagnosis code from an inpatient visit, or at least two occurrences of a UC diagnosis code from outpatient vists, with at least one of the two outpatient codes documented by a gastrointestinal specialist. UC codes assigned on different dates do not need to be the same to qualify. At least 12 months of continuous (i.e., no more than a 30-day gap) database enrollment before index date is required to enable analysis of baseline patient and disease characteristics that may be important modifiers of the relationship of UC with safety endpoints of interest. Index date is defined in the treatment cohort inclusion criteria listed in the subsections below.

ICD-9 Code	Diagnosis	ICD-10 code	Diagnosis
556 (no 3 rd digit)	Ulcerative colitis		
556.0	Ulcerative enterocolitis	K51.8 (all billable codes under K51.8)	Other UC
556.1	Ulcerative ileocolitis	K51.8 (all billable codes under K51.8)	Other UC
556.2	Ulcerative proctitis	K51.2 (all billable codes under K51.2)	Ulcerative (Chronic) Proctitis
556.3	Ulcerative proctosigmoiditis	K51.3 (all billable codes under K51.3)	Ulcerative (Chronic) Rectosigmoiditis
556.5	Left-sided ulcerative colitis	K51.5 (all billable codes under K51.5)	Left Sided Colitis
556.6	556.6 Universal ulcerative colitis		Ulcerative (Chronic) Pancolitis
556.8	Other ulcerative colitis	K51.8 (all billable codes under K51.8)	Other Ulcerative Colitis
556.9	Ulcerative colitis, unspecified	K51.9 (all billable codes under K51.9)	Ulcerative Colitis, Unspecified

Table 1. ICD Codes for UC Diagnoses within MarketScan Database

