9.2.1.2.1. Cohort 1 (Tofacitinib cohort): Adult UC Patients Treated with Tofacitinib

1. Initiation of tofacitinib as captured in Marketscan since 30 May 2018 (i.e. first tofacitinib prescription occurring either after the first UC diagnosis code from an inpatient visit or after the second UC diagnosis code from an outpatient visit and following US approval of tofacitinib for UC).

Note that in the US, as per the US prescribing information (USPI), tofacitinib is not expected to be prescribed to newly diagnosed UC patients, and since UC is a chronic condition, it is expected that the majority of UC patients receiving tofacitinib would have previously been prescribed other forms of UC therapy. For those patients with

an outpatient diagnosis of UC, it is unlikely that many, if any at all, will receive a prescription for tofacitinib after the first UC diagnosis code (and before the second UC diagnosis code).

2. Patients with either 1 UC diagnosis code from an inpatient visit or ≥2 of any of the ICD-10 codes for UC in Table 1 from an outpatient visit prior to the index date (i.e. date of first prescription of tofacitinib) (at least one of the two required UC diagnoses from outpatient visits must be made by a gastrointestinal specialist.

As per recommendations from the USPI, patients in this cohort may not be on potent immunomodulators/immunosuppressants concurrently.

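### Section 9.3.2 accepts ulcerative colitis as an on-label indication on weaker outpatient evidence than the other three indications and than the protocol's own UC definition

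*Protocol*

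**What the plan says.** Section 9.3.2 classifies each patient's indication at the first tofacitinib prescription as on-label, off-label or unknown. Section 9.3.6 makes this the main utilization endpoint. All four indications can be met with one inpatient code. The outpatient routes differ:

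- RA: at least two "outpatient RA diagnosis codes on two unique calendar days, with at least one from a rheumatologist".
- PsA: at least two "outpatient PsA diagnosis codes on two unique calendar days, with at least one from a rheumatologist".
- pcJIA: at least two "outpatient pcJIA diagnosis codes on two unique calendar days, with at least one from a rheumatologist".
- UC, May 2018 to July 2019 (item 4 of the list): "defined as the first UC diagnosis code from an inpatient visit or after the second UC diagnosis code from an outpatient visit".
- UC, after July 2019 (item 5): the prescription must have "occurred after a diagnosis of UC (as defined above) AND after evidence of prior TNFi use", so the definition in item 4 carries over.

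The dose criteria in the same section also refer back to these diagnosis definitions.

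Elsewhere the protocol defines outpatient UC more strictly. Section 9.2.1.2 wants two outpatient codes "with at least one of the two outpatient codes documented by a gastrointestinal specialist". For Cohort 1, section 9.2.1.2.1 says that "at least one of the two required UC diagnoses from outpatient visits must be made by a gastrointestinal specialist". Cohorts 2 to 4 and the patient count in section 9.5 carry the same condition.

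**The concern.** One protocol holds two case definitions for one disease, and the looser one feeds the main utilization endpoint. No reason is given for treating UC differently from RA, PsA and pcJIA. Section 9.9 warns that a claims code may be wrong or may record a diagnosis that was only being ruled out. Specialist and separate-day conditions are the usual guard against such codes, and UC alone lacks both.

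The dose analysis is exposed as well. UC is the only indication for which 10 mg twice daily and 22 mg once daily count as on-label dose, and section 7 names possible use of these regimens in non-UC patients as a reason for the study. The UC maintenance-dose proportions and the proportion of TNFi-naïve UC patients in section 9.7.1 also depend on who counts as a UC patient.

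**Working it through.** The protocol gives no figure on this point, so the check sets the rules side by side and follows typical patients through them.

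**Outpatient route by rule**

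| Rule | Codes | Separate days | Specialist code |
|---|---|---|---|
| RA, PsA, pcJIA (9.3.2) | 2 or more | required | rheumatologist |
| UC, utilization (9.3.2, items 4 and 5) | 2 | not stated | not stated |
| UC, surveillance (9.2.1.2 and Cohorts 1 to 4) | 2 or more | not stated | gastrointestinal |
| UC, patient count (9.5) | 2 or more | not stated | gastrointestinal |

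The specialist condition is missing in one row only, and that is a contradiction within the protocol. The separate-day condition is absent from every UC rule. On dates, section 9.2.1.2 says only that "UC codes assigned on different dates do not need to be the same to qualify", which does not require different dates. The two-day gap is therefore a difference from the other three indications, not from the surveillance definition.

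**Patients followed through the rules**

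1. *Adult with two outpatient UC codes, none from a gastrointestinal specialist, first prescription between May 2018 and July 2019.* Item 4 is met, so the patient is on-label UC. Under 9.2.1.2 the same patient does not have UC.
2. *The same patient, first prescription after July 2019, with any earlier TNFi.* Item 5 is met. The prior TNFi need not have been given for UC.
3. *RA patient with two such UC codes and a later 10 mg twice daily prescription.* The indication is on-label through RA in any case, so the indication split does not change. The prescription, however, follows a UC diagnosis as 9.3.2 defines it and can be scored as on-label dose.
4. *Crohn's patient with two non-specialist outpatient UC codes (and a prior TNFi if after July 2019).* On-label UC today. If only items 4 and 5 are tightened, the patient leaves on-label but cannot become off-label, because 9.3.2 describes off-label patients as lacking any RA, PsA, UC or JIA code. On a literal reading the patient becomes unknown.
5. *Crohn's patient with two outpatient UC codes on separate days, one from a gastroenterologist, or with one inpatient UC code (and a prior TNFi if after July 2019).* On-label UC before and after the tightening.
6. *True UC patient with two outpatient codes and no recorded specialist (and a prior TNFi if after July 2019).* Correctly on-label today; unknown after the tightening.

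**Size.** Section 9.5 counts 59,080 UC patients in 2016–2018 data, but under the specialist definition. No count under the looser definition is given, and no sensitivity or specificity for either. Patients 1 to 4 show false UC being accepted, and patient 6 shows true UC that the stricter rule would lose. The balance between them cannot be computed.

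**The case against.** The strongest defence is that the UC wording in 9.3.2 is shorthand for timing. Section 9.2.1.2.1 uses nearly the same phrase in its first item to place the prescription after diagnosis, and adds the specialist condition in its second. Section 9.3.1 dates UC onset in the same way, and section 9.3 leaves detailed definitions to the SAP. An incomplete carry-over is indeed plausible. But 9.3.2 presents the phrase as the definition of UC, states that the criteria are those for this analysis, and refers back to it later. Section 9.7 adds that major changes to endpoint definitions belong in a protocol amendment.

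The scope is also limited, and that stands: the UC rules apply only from May 2018, and after July 2019 prior TNFi use is required as well.

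A reader might infer more than the document supports:

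- *That the loose rule is what lets Crohn's use pass as UC, and that a specialist code would stop it.* Patients 4 and 5 show otherwise. A gastroenterologist may code either disease, the inpatient route stays open, and the off-label clause blocks reclassification.
- *That the on-label share is overstated, point for point, by everyone who qualifies only on weak codes.* Patient 6 is correctly on-label now, and patient 3 is on-label through another indication.
- *That the surveillance definition contains a two-day rule which 9.3.2 drops.* It does not.
- *That being UC under Research Question 1 but not under Research Question 2 is in itself an error.* The two populations differ by design: surveillance requires adults with 12 months of prior enrolment, and utilization has no exclusions.

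**Conclusion.** The inconsistency is real and should be corrected. UC is the only one of the four indications accepted on two outpatient codes without a specialist code or separate days, and this conflicts with the specialist requirement that the protocol applies to outpatient UC elsewhere. The looser rule passes into item 5 and the UC dose criteria, so it reaches both the indication split and the off-label dosing proportions.

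The conclusion rests on reading 9.3.2 as written. The missing specialist condition is the firmer part. The missing separate days are weaker, since a second code may have been meant as a second visit. The effect may be small or material: the document allows no estimate of its size, and no statement of its net direction against the truth.

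**What to change.** In 9.3.2, items 4 and 5, and by reference in the dose criteria:

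- Define UC as at least one inpatient code, or at least two outpatient codes with at least one from a gastrointestinal specialist, as in 9.2.1.2.
- Add the condition of two unique calendar days already used for RA, PsA and pcJIA. This is new for UC, since the surveillance definition does not contain it.
- In the off-label clause, replace the absence of any UC code by not meeting the UC definition.
- State how patients with both Crohn's and UC codes are classified, and report their number.
- Show the looser UC definition as a sensitivity row.

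The cost is a few sentences and one extra table row. The specialist condition must be programmed for the surveillance part anyway; the two-day check is a small addition. Some true UC patients without a recorded specialist code will move to unknown, and the sensitivity row will show the combined effect of the stricter rule. Crohn's patients coded as UC by a gastroenterologist or on an inpatient claim are still not removed by the tighter code rule, which is why the rule for dual-coded patients and their count are needed.
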